It is clear that we need better tools against emerging pandemic threats. In the current approach we can first act only once we have identified the new pathogen; then we can start to develop new vaccines or new forms of treatment. This may take a long time before such measures are approved. If this RCT provides us with evidence of protective NSEs against COVID-19, we will not only have a tool against COVID-19, but likely also a tool that may help protect against other emerging pandemics in the future.

The current pandemic, COVID-19, seriously challenges the available hospital capacity and this is augmented by absenteeism of HCWs. HCWs are at high risk, as they constitute over 20% of all the COVID-19 cases in countries with available data. Strategies to prevent absenteeism of HCW are therefore desperately needed. This study contributes to that goal.

Elderly are another vulnerable group of the COVID-19 pandemic. If BCG protects COVID-19 in HCW, it will be an obvious next step to expand its use to other population groups.

Additionally, if BCG proves useful against COVID-19 it would be yet another confirmation that it strengthens the immune system against unrelated pathogens. While it is not a given that it will work against any kind of pathogen, we have so far seen BCG protects against viruses, bacteria as well as parasite infections.

Hence, there is reason to believe that it works against a large range of pathogens. Our results will provide further scientific evidence of these non-specific effects of BCG with relation to our central hypothesis that BCG (re)vaccination may induce (partial) protection against susceptibility to and/or severity of COVID-19.

Withdrawal from the study

Subjects can leave the study at any time for any reason if they wish to do so, without any consequences. The investigator can decide to withdraw a subject from the study for urgent medical reasons.

COVID-19 diagnosis and treatment

In case of suspicion of COVID-19, the national guidelines for testing and treatment of patients will be followed.

Public disclosure and publication policy:

The results of this study will be disclosed unreservedly at the end of the study. Results that are important for public health will be notified to the competent authorities as swiftly as possible. The trial will be registered in a public trial registry before the first patient is recruited.

REFERENCES

Based on the capacity of BCG to: 1) reduce the incidence of respiratory tract infections and mortality in children and perhaps in the elderly; 2) exert antiviral effects and reduce viremia in an experimental human model of viral infection, we hypothesize that BCG vaccination may induce partial protection against susceptibility to and/or severity of COVID-19 and other infections which might result in a reduction in the number of days of unplanned absenteeism from work for HCW. The underlying hypothesis for this study is that BCG vaccination of HCW reduces unplanned absenteeism due to illness by 20%.

Objectives

Primary: Test the capability of BCG to reduce absenteeism due to illness among HCW working at a health care facility that treats patients who could suffer from COVID during the COVID-19 pandemic. Secondary: reduce number of HCW that develop COVID-19; ii) reduce number of hospital admissions due to illness of HCW during the COVID-19 pandemic.

Trial design

Single-blind, parallel-group placebo-controlled multi-centre block randomized trial including a total of 1050 HCW. The study sites were the Manhiça District Hospital and Mavalane General Hospital in Mozambique, and Hospital Nacional Simão Mendes and other hospitals in the capital Bissau in Guinea-Bissau.

Unfortunately, Cape Verde was not authorized to conduct the study, because there is no existing legislation regulating clinical research in the country. As so, the number of the sample size in Guinea Bissau and in Mozambique was increased from 350 to 525 to guarantee the inclusion of the 1050 participants.

Study population. Health Care Workers (HCW) defined as a person who delivers care and services to the sick and ailing either directly as doctors and nurses or indirectly as aides, helpers, laboratory technicians, or even medical waste handlers.

Exclusion criteria

Known allergy to (components of) BCG or serious adverse events to prior BCG administration; known previous, active or latent infection with *Mycobacterium tuberculosis* or other mycobacterial species, fever (>38 C) within past 24 hours; previous confirmed COVID-19 (positive test by PCR or antibody) until inception of COVID-19 vaccination of HCW; suspicion of active viral or bacterial infection, severely immunocompromised subjects, self-reported HIV infection (Guinea: HIV-rapid test), self-reported pregnancy; active solid or non-solid malignancy or lymphoma within the last two years; any other contraindications for live-attenuated vaccine administration, not having a telephone.

Randomization

All participants who give consent for participation and who fulfil the inclusion criteria will be randomly assigned to either placebo or BCG group with a 1:1 (treatment:placebo) allocation in varying block sizes of 4 or 6 per block within strata defined by gender (male/female) and occupational group (doctors/nurses/other).

Blinding

The BCG vaccine was administered by study physicians/nurses, who are not blinded but also not involved in the data collection. Participants and follow-up assistants will be blinded to the treatment allocation. In case of serious adverse events, the participant can be unblinded after consultation with the investigator or the vaccinating physician/nurse. When the study has ended, all participants will receive information about the intervention that they received.

Intervention

The intervention consists of the administration of an intradermal injection of a standard 0.1 ml adult dose of attenuated *Mycobacterium bovis* BCG (Bacillus Calmette-Guerin), Danish strain 1331, $2-8 \times 10^5$ CFU or the placebo comparator: intradermal standard 0.1 ml saline solution (NaCl 0.9%). Both BCG and saline solution will be injected in the skin over the upper deltoid muscle.

Outcomes

Primary outcome measure: Total numbers of days of unplanned absenteeism from work due to illness.

Secondary outcome measures: Days of unplanned absenteeism because of documented COVID-19 and cumulative incidence of hospital admissions due to illness (minus accidents).

Other Outcomes Measures: Hospitalisation for COVID-19; hospitalisation for respiratory infections; COVID-19 infection episodes; Furthermore, we will study the effect on Death for any reason, Death due to documented COVID infection. Cumulative incidence of infectious disease episodes, in particular respiratory infections. Cumulative incidence of infectious hospital admissions, in particular respiratory infections. Cumulative incidence of hospital admission due to documented COVID-19. Cumulative incidence of all-cause and infectious intensive care admission. Cumulative incidence of intensive care admission due to documented COVID infection.

Baseline data collection

Enrolment data regarding chronic illnesses and treatment, lifestyle (family structure, socioeconomic factors, smoking), vaccination history including previous BCG vaccination. Blood sample for SARS-CoV-2 serology.

Follow-up

Follow-up will last for 6 months (182 days). Telephone interviews every second week, regarding symptoms, absenteeism and causes, COVID-19 testing (if done) and their results. Supplemented by daily workplace presence registry information (where present).

End of follow-up

At the end of follow-up, participants will be invited back to the room of the healthcare facility where they were recruited to have another SARS-COV-2 antibody test and to complete the final questionnaire; also, at this time, the research officer will be asked to inspect and report how scarification is in the deltoid area of the right upper limb of the HCW, which may occur due to the BCG vaccine. Information regarding the treatment (BCG or placebo) will be disclosed to the participant at this time.

Sample size

The sample size was calculated on the basis of the primary hypothesis. A total of 1050 HCW randomized with an estimated loss to follow-up of 5%, and a mean number of days off work due to illness in the control group of 5 days (SD=5) over a 6-month period will demonstrate a reduction among BCG vaccinated of 20% for a mean absence of 4 days (80% power and alpha 0.05). The estimated loss to follow-up (5%) was based on past telephone-based surveys conducted in Bissau.

Statistical analysis.

Data will be reported quantitatively. All analyses will be performed from the intention-to-treat principle. Missing data on background variables will be dealt with by multiple imputation. Final data analysis will begin when the last participant in the multicentric RCT has completed the follow-up period. The primary endpoint, work absenteeism due to illness, will be reported as the total number of sick days with standard deviation. Continuous baseline characteristics will be reported as means with the standard deviation or medians with the inter-quartile range, as appropriate. Categorical baseline characteristics will be reported as count and percentage. Statistical testing for baseline characteristics will be performed. Days of absenteeism will be analysed using a Bayesian negative binomial regression with a fixed effect for BCG, hospital, professional category, age, enrolment week and number of average workdays per week. Incidence data will be analysed in Cox proportional hazards models. Monthly, data on absenteeism by randomization group will be reported to the DSMB.

Trial registration

The trial is registered at clinicaltrials.gov. (<https://clinicaltrials.gov/ct2/show/NCT04641858>)

Funding

EDCTP is funding the run-in costs for the BCG-COVID-RCT, including trials in the respective countries and for training and management.

Study management, monitoring and quality control

The project is led by an International Steering Committee (ISC) consisting of PIs in each of the five countries involved: [name] (international coordinator), PI from Denmark; [name], PI from Guinea-Bissau; [name], PI from Portugal; [name], PI from Cape Verde; and [name], PI from Mozambique. The overall coordination is the responsibility of the Danish partner. The leader has extensive leadership experience from running a Center of Excellence in Denmark and the research group of the Bandim Health Project in Bissau for many years. The Bandim Health Project has a history of past collaboration with the Portuguese partner. The research group will hold teleconferences at least once a week with a formal pre-established agenda on training, enrollment, follow-up, losses to follow-up, staff turnover, vaccine logistics, quality control of data collection, data entry and database management, interim analysis, communication and dissemination activities, other risks. Decisions from each meeting are recorded by the coordinator.

2. Definitions

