- Ensuring vaccine supply - We will procure vaccines locally, rather than relying on flying in vaccines specifically for the trial. This may give variability in vaccine type available (supply can be from several UNICEF-pre-qualified producers). However, in the current situation with limited shipping possibilities for research, we find this the best, pragmatic solution. If producers are different in the different sites, this will be noted, and we will scrutinize data for signs of differences in effect by producer. Essentially, this trial will address the research question of relevance for Africa now: can we use the BCG available to mitigate the pandemic.

Quality management

Quality management activities include recruitment of a Data Safety and Monitoring Board (DSMB), who are actively involved in the project, approving the quality of the project outputs, including deliverables and dissemination, and supporting the consortium in key decisions taken within the project, while maintaining their independence. Furthermore, each site will recruit an internal monitor, who will conduct at least two monitoring visits during the conduct of the trial.

ETHICS

The protocol for this study follows standard clinical trials ethical approval procedures for each country. In Mozambique, the study protocol was first approved by the CISM Committee for Bioethics in Health on the 26th of October 2021, approval number CIBS-CISM/079/2020. Approval by the National Committee on Bioethics in Health (Comité Nacional de Bioética para a Saúde), was given on March 11 2021 with approval number Ref: 115/CNBS/21. A protocol amendment regarding changes in inclusion criteria was approved on June 21, 2021 with approval number Ref: 347/CNBS/21. In Guinea-Bissau, the study protocol was approved by the Ethics Committee for Research (Comité Nacional de Ética na Saúde) on November 3 2020 with approval number 119/CNES/INASA/2020.

In Denmark, the study protocol was given consultative approval by the National Ethics Committee on November 2, 2020, approval number 2015556. In Portugal and Denmark, no local ethical approval is required as long as the study protocol is approved by the Ethics Committees of the countries where the study is to be conducted.

Ethical approval and legal documentation will be kept by the PI of the respective country.

Recruitment, inclusion and exclusion criteria and informed consent procedures.

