2.2. Analyzed populations

The clinical trial participants are 1,050 HCW (definition below) recruited from hospitals in two different African countries.

The Guinea-Bissau arm of the BCG-COVID-RCT study is conducted in Bissau, the country capital, by the Bandim Health Project (BHP). The team is led by [name]. Inclusions commenced in Guinea-Bissau on December 3rd, 2020, in the Hospital Nacional Simão Mendes. After concluding inclusions at Simão Mendes, inclusions were commenced at other hospitals and health centers.

In Mozambique, this study is being conducted at Manhiça District Hospital (MDH) and Mavalane General Hospital (MGH) by the Centro de Investigação em Saúde de Manhiça (CISM) through the team led by [name]. Manhiça District Hospital is located on the main National Road One, in the capital of the Manhiça district, Maputo Province, southern Mozambique. Manhiça is a rural area located approximately 80km away from the capital, Maputo city; has a total population close to two hundred thousand people. MDH is the referral hospital with more than 100 beds and absorbs the largest proportion of HCW within the district. MGH (260 beds) is located in the district of neighborhood of Mavalane, in Maputo city (Southern Mozambique). The MGH is part of the three general hospitals of the city of Maputo. The health

area of Mavalane is the largest in the city and serves an estimated population of 609.889 inhabitants, about 50% of the health population of the capital of nation capital.

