Primarily a descriptive analysis will be performed of all information contained in the two study groups (BCG and placebo). All variables will be analysed, one by one, to know their distribution. Background factors will be summarised by counts (percentages), means (standard deviation) or medians (interquartile range) as appropriate. Proportions will be compared using the chi-square test - χ^2 test or Fisher's Exact test (categorical variable) or Student's t-test or Mann-Whitney test (quantitative variable) according to the distribution of variables. Statistical significance was set at the 5% level (two-tailed tests) and 95% confidence intervals (95%CI) for the estimates.

The endpoints variables (table 1) will be analyzed using univariate analysis (Logrank test) and Multivariate analysis (Cox Proportional Hazard Regression, or Cox Regression), stratified by the block randomization variables gender (male/female) and occupational group (doctors/ nurses/other) in addition to site. Covariates will be tested in the model univariate, and only those that were associated with the outcome at a significance level of at least 20% will be retained in a possible multivariate model. A significance level (p-value) of less than 0.05 and its respective confidence intervals (CI) will be used.

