When you have a small sample and the numerical variable is not known to have a normal distribution (or cannot be verified satisfactorily), or when there is no homogeneity of variances, Student's t-test is not appropriate. In this situation, the nonparametric Mann-Whitney test (Wilcoxon rank-sum test, U-test) can be used. Unlike the t-test, which tests for equality of means, the Mann-Whitney test tests for equality of medians. The U values calculated by the test assess the degree of intermingling of the data of the two groups after sorting. The greater separation of the data together indicates that the samples are distinct, rejecting the hypothesis of equality of the medians. Total days of absenteeism will be analyzed using a Bayesian negative binomial regression with a fixed effect for BCG, hospital, professional category, age, enrolment week and number of average workdays per week. The excess absence of the event of interest can lead to data overdispersion (a phenomenon that occurs when the variance of the response variable is greater than the value of the mean). To check the overdispersion of the data we will use the deviance, which is also a statistic used to check the goodness of fit of the model.

The Kaplan-Meier method consists of dividing the follow-up time into intervals, whose limits correspond to the follow-up time when events occurred. The measure of association used in survival analysis to

compare groups is the Hazard Ratio (HR), with similar meaning to Relative Risk; HR is the probability that some participant who did not have the outcome event by a certain time, will have it at that time. HR therefore compares the instantaneous incidence with which events occur in the different groups (BCG and Placebo).

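### The prior-COVID-19 exclusion lapsed during enrolment, but baseline antibody result and COVID-19 vaccination are not named in the absenteeism models and no BCG effect by baseline immune status is planned

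*SAP*

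**What the plan says.** **Eligibility.** The SAP's Exclusion criteria bar workers with "previous confirmed COVID-19 (positive test by PCR or antibody) until inception of COVID-19 vaccination of HCW". No calendar date is given for either country. SAP 2.2 gives the start of enrolment: "Inclusions commenced in Guinea-Bissau on December 3rd, 2020, in the Hospital Nacional Simão Mendes". The protocol's Ethics section reports for Mozambique that "A protocol amendment regarding changes in inclusion criteria was approved on June 21, 2021", without saying what changed. The exclusion is absent from all three eligibility lists in the protocol: the abstract, the inclusion and exclusion criteria, and the Ethics text on recruitment.

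**Data collected.** The SAP's Baseline data collection includes "Blood sample for SARS-CoV-2 serology". Protocol Recruitment and SAP section 4 describe a point-of-care antibody test at enrolment. SAP Table 2 has rows for COVID-19 vaccine (yes/no), type and dose, but none for the baseline antibody result.

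**Model.** The SAP's Statistical analysis section specifies a "Bayesian negative binomial regression with a fixed effect for BCG, hospital, professional category, age, enrolment week and number of average workdays per week". SAP 6.4 and the protocol's Data analysis section give the same covariates. The shorter list in the protocol abstract names neither antibody result nor vaccination. SAP Table 4 reports one RR for each absenteeism endpoint.

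**A second route.** SAP 6.1 also states: "The endpoints variables (table 1) will be analyzed using univariate analysis (Logrank test", followed by Cox regression stratified by gender, occupational group and site. On that route, "Covariates will be tested in the model univariate, and only those that were associated with the outcome" at the 20% level are kept.

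**The concern.** The hypothesis in both documents works partly through susceptibility to, and severity of, COVID-19. Workers already infected or vaccinated plausibly have less COVID-19 absence for BCG to prevent. The lapse of the exclusion lets such workers in part-way through, and the trial holds the two baseline measurements that identify them.

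Two things follow. First, a baseline variable that predicts absence, and is already collected, is left out of the named adjustment set. That matters most for days absent because of documented COVID-19, the first-listed secondary outcome. Second, if the pooled RR is weak, the plan has no prespecified estimate showing whether the effect differs by baseline immune status. An analysis chosen after the data are seen would carry little weight.

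**Working it through.** **1. Text check.** Antibody result and COVID-19 vaccination appear in none of the stated covariate lists for the negative binomial model. They are not randomisation strata, which are gender and occupational group. No subgroup or interaction by serostatus, vaccination or eligibility period was found. The only check of effect modification found is by BCG producer, in the protocol's list of risks.

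**2. Inputs.** From the sample size sections: 1050 randomised, 5% loss, control mean 5 days, SD 5, target RR 0.80. So 1050 × 0.95 = 997.5 analysed, or 498.75 per arm. For a negative binomial, variance = mean + mean²/k, so k = 25/(25 − 5) = 1.25. With RR 0.80 in everyone, the SE of log RR is √[(1/5 + 1/4 + 2/1.25)/498.75] = 0.0641. Power is Φ(0.2231/0.0641 − 1.96) = 94%, which is the reference below. The plan gives no figure on this point, and no share previously infected or vaccinated, so every immune share and ratio below is an assumption.

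**3. Bias and precision when the BCG effect is constant.** Negative binomial totals were simulated with true RR 0.80 and half the workers immune.

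| Sick days, immune / susceptible | RR, covariate omitted | RR, adjusted | SE, omitted | SE, adjusted |
|---|---|---|---|---|
| 0.7 | 0.801 | 0.802 | 0.065 | 0.064 |
| 0.5 | 0.798 | 0.796 | 0.068 | 0.065 |
| 0.3 | 0.802 | 0.801 | 0.075 | 0.066 |

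Omission does not bias the RR. At ratio 0.7, with 20%, 40% and 60% immune, the SE goes from 0.0650 to 0.0645, 0.0660 to 0.0651 and 0.0667 to 0.0658. These are gains of 0.8%, 1.4% and 1.3%.

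For COVID-19 absence, assuming a mean of 2 days, k = 0.2 and an immune rate 0.3 times the susceptible rate, adjustment lowers the model SE by about 2–4% and the empirical SE by about 6–12%.

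**4. Dilution, worst case.** Assume RR 0.80 in susceptible workers, RR 1.0 in immune workers, immune workers with 0.7 times the sick days, and immune share p. Then pooled RR = [0.8(1 − p) + 0.7p] / [(1 − p) + 0.7p].

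- p = 0.2: 0.78/0.94 = 0.830
- p = 0.4: 0.76/0.88 = 0.864
- p = 0.6: 0.74/0.82 = 0.902

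For power, take a susceptible control mean of 5 days. The relative variance in an arm with mean μ is 1/μ + 1/k + (1 + 1/k) × (variance of the two group means)/μ². Adding the two arms and dividing by 498.75 gives SEs of 0.0649, 0.0656 and 0.0661. Power is then about 82%, 61% and 34%, against 94%.

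**5. Dilution, milder case.** Suppose instead that BCG acts only on COVID-19 absence, with the same relative effect in both groups. The ratios 0.7 (all absence) and 0.3 (COVID-19 absence) imply that COVID-19 makes up 0.3/0.7 = 43% of susceptible workers' absence. An overall RR of 0.80 then needs a 0.20/0.43 = 47% cut in it. In immune workers the RR is 1 − 0.06/0.70 = 0.91. Pooled RRs are 0.768/0.94 = 0.82, 0.736/0.88 = 0.84 and 0.704/0.82 = 0.86.

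**6. What an interaction can show.** Take RR 0.80 against 1.00, equal control means of 5 and a 50:50 split. The variance is (0.20 + 0.25 + 1.6)/249.375 + (0.20 + 0.20 + 1.6)/249.375 = 0.01624, so the SE is 0.127. Power is Φ(0.2231/0.127 − 1.96) = 42%. It is 33% with a 25:75 split either way, and about 18% at 10:90.

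**The case against.** The case on the other side is strong, and much of it stands.

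- **Validity.** A reader might infer that the pooled RR is biased or invalid. It is not: under randomisation it is the average effect in those enrolled, and step 3 shows no bias from omission. The lapse is also tied to calendar time, and enrolment week and hospital are in the model. They do not, however, separate immune from susceptible workers enrolled in the same week and hospital, or let the BCG effect differ.
- **Adjustment alone.** Adding two main effects would still give one RR. Only an interaction or group-specific estimates show whether the effect differs.
- **Other models.** A reader might conclude that no model could contain these variables. The 20% screen on the Cox route in SAP 6.1 could admit either one. It is data-driven and does not belong to the negative binomial model, so the supportable statement is that neither is named there.
- **Who can benefit.** It is tempting to say that later enrollees could not benefit. The SAP hypothesis covers other infections too, and the primary outcome is absence for any illness. The protocol's risk list calls the serology analysis not central to the absenteeism objective.
- **Clean separation.** The later cohort can also include antibody-negative, unvaccinated workers. With 182 days of follow-up, early enrollees may be vaccinated after randomisation. Baseline status does not reproduce the eligibility periods.
- **Protocol mismatch.** The protocol is dated January 2022, after the Mozambique amendment, and may simply omit a lapsed criterion. It cannot be called a contradiction, but a reader cannot tell who was eligible when.

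**Conclusion.** The point holds as a gap in adjustment and prespecification, not as a flaw in the validity of the primary estimate. Eligibility with respect to prior COVID-19 changed during enrolment. Two baseline measurements that bear on it are collected, but the absenteeism model does not name them and no effect by immune status is planned.

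The precision cost is about 1% of the SE on the primary endpoint. It is larger for COVID-19 absence, under assumed inputs. The interpretive cost depends on the immune share and on how far the BCG effect differs, neither of which the documents give. Pooled RRs of 0.83, 0.86 and 0.90 are a worst case with no BCG effect in immune workers. The milder case gives 0.82, 0.84 and 0.86, and dilution is smaller again if BCG also prevents other infections.

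A reader might expect a subgroup estimate to settle whether a weak result means dilution or no effect. With interaction power of about 33–42% even under the assumed 0.80 versus 1.00 contrast, it will not do so reliably. Its value is a prespecified description.

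**What to change.** 1. Add baseline antibody result and COVID-19 vaccination before randomisation (yes/no) as fixed effects in the negative binomial models for total and for COVID-19 absenteeism.
2. Prespecify one BCG-by-baseline-immune-status estimate: RRs with intervals in antibody-negative, unvaccinated workers and in all others. Label it exploratory and low-powered. Do not use vaccination received after randomisation to define the groups.
3. Add the baseline antibody result to SAP Table 2, and state when the exclusion lapsed in each country.
4. Reconcile the SAP's Exclusion criteria with the three eligibility lists in the protocol, so that the criterion in force at each time is clear.

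The cost is SAP and protocol wording, two extra model terms and one short table, from data already collected. The subgroup estimates will be imprecise and must not be read as confirmatory.
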